9.4.7.3 Pharmacokinetic Evaluation

Plasma samples will be assayed for idronoxil and up to 7 selected metabolites by validated LC-MS/MS. Individual plasma concentration-time data and plasma PK parameters will be summarized using descriptive statistics by treatment day and sampling time for idronoxil and the 7 detectable metabolites (GIS/SIG, IG, GI, IS, SI, SIS, and GIG). Plasma PK parameters will be determined by noncompartmental analysis for idronoxil and selected metabolites (SI, IS, GI, IG, SIG/GIS, GIG, SIS) and will be summarized by dose and treatment day.

The following PK parameters will be estimated for idronoxil and the selected metabolites following the morning dose on Days 1, 6 and 14 of Cycle 1, as data permit: C_{max} , C_{min} (predose), T_{max} , $AUC_{(0-t)}$, $AUC_{(0-6)}$, $AUC_{(0-12)}$, $AUC_{(0-inf)}$ and $t_{\frac{1}{2}}$. Details of the analyses will be included in the SAP.

Dose proportionality will be assessed using the power model for C_{max} , $AUC_{(0-t)}$, $AUC_{(0-inf)}$, $AUC_{(0-6)}$, and $AUC_{(0-12)}$ on Days 1, 6 and 14 of Cycle 1 for the parent compound.

If data permits, accumulation ratios will be calculated for parent compound and selected metabolites for C_{max} , C_{min} , $AUC_{(0-t)}$, $AUC_{(0-inf)}$, $AUC_{(0-6)}$, and $AUC_{(0-12)}$ for Days 6 and 14 of Cycle 1 (e.g., Day 14/Day 1 and Day 6/Day 1) and Day 8 of Cycles 2 and 3.

The metabolite to parent ratios will be calculated (as data permit) for Days 1, 6 and 14 of Cycle 1, for $AUC_{(0-t)}$, $AUC_{(0-inf)}$, $AUC_{(0-6)}$, and $AUC_{(0-12)}$ and for single time points on Day 1 of Cycles 2 and 3.

Concentration and PK parameter data will be listed, summarized and plotted. Details of these analyses will be included in the SAP.

There are no formal PK parameters for concentration data from Cycles 2 and 3 because these are single time points. However, metabolite to parent ratios will be explored.

Exploratory analyses of the relationship between plasma concentrations of parent drug and selected metabolites and/or PK parameters and AEs or PD biomarkers may be assessed by graphical methods and special summary tables. Exposure-response relationship may also be explored.

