1.1 Synopsis

Protocol Title: A Phase 1b/2a Multicenter Study of NOX66 and External Beam Radiotherapy in Patients with Metastatic Castration-resistant Prostate Cancer and Other Solid Tumors

Sponsor Protocol No.: NOX66-005

Development Phase: Phase 1b/Phase 2a

Sponsor: Noxopharm Limited

Study Sites and Locations: Approximately 14 sites in Australia, United States and Europe

Rationale:

Idronoxil, which is the active ingredient of the NOX66 formulation, is a synthetic flavonoid derivative of genistein that inhibits external Ecto-NOX disulfide-thiol exchanger (ENOX) 2 to induce apoptosis. ENOX2 inhibition activates the sphingomyelinase pathway and deactivates the antiapoptotic protein kinase B pathway, a key driver of radiotherapy resistance. The targeted effect on ENOX2 has the potential to limit toxicity to non-cancer cells, which preferentially express ENOX1. Previous studies have demonstrated improved radiation sensitivity in prostate cancer with flavonoid derivatives. Early studies of intravenous and oral formulations of idronoxil were hampered by limited bioavailability. The Sponsor has sought to address the problem of extensive drug metabolism through the development of a rectal suppository dosage form. With blood draining from the distal part of the rectum directly into the inferior vena cava, first pass liver metabolism can be avoided. In the case of a diphenolic drug such as idronoxil, the bioavailability is augmented by the rectal mucosa being known to be devoid of transferase activity and therefore the phase II metabolism is significantly reduced. These two aspects combined are the basis for the rationale that idronoxil delivered via the rectum is subjected to less phase I and phase II metabolism than that observed for orally administered idronoxil. NOX66 is a suppository dosage form of idronoxil in a proprietary fatty base containing a surfactant. This formulation is novel in that a lipophilic active ingredient is dispersed in a lipophilic suppository base - compared with traditional suppository formulations whereby a hydrophilic base would normally be utilized. Moreover, this suppository dosage form provides a slow and sustained release of idronoxil comparable to an intravenous infusion.

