Plasma samples will be assayed for idronoxil and up to 7 selected metabolites by validated high-performance liquid chromatography and mass spectrometry methodology. Individual plasma concentration-time data and plasma PK parameters will be summarized using descriptive statistics by treatment day and sampling time for idronoxil and the 7 detectable metabolites (GIS/SIG, IG, GI, IS, SI, SIS, and GIG). Plasma PK parameters will be determined by noncompartmental analysis for idronoxil and selected metabolites and will be summarized by dose and treatment day.

- The following PK parameters will be estimated for idronoxil and the selected metabolites following the morning dose on Days 1, 6 and 14 of Cycle 1, as data permit: C_{max}, C_{min} (predose), T_{max}, AUC_(0-t), AUC₍₀₋₆₎, AUC₍₀₋₁₂₎, AUC_(0-inf) and t_{1/2}.
- Dose proportionality will be assessed for C_{max} , $AUC_{(0-t)}$, $AUC_{(0-inf)}$, $AUC_{(0-6)}$, and $AUC_{(0-12)}$ on Days 1, 6 and 14 of Cycle 1 for the parent compound.
- If data permits, accumulation ratios will be calculated for parent compound and selected metabolites for C_{max}, C_{min}, AUC_(0-t), AUC_(0-inf), AUC₍₀₋₆₎, and AUC₍₀₋₁₂₎ for Days 6 and 14 of Cycle 1 (e.g., Day 14/Day 1 and Day 6/Day 1) and Day 8 of Cycles 2 and 3.
- The metabolite to parent ratios will be calculated (as data permit) for Days 1, 6 and 14 of Cycle 1, for AUC_(0-t), AUC_(0-inf), AUC₍₀₋₆₎, and AUC₍₀₋₁₂₎ and for single time points on Day 1 of Cycles 2 and 3.

Concentration and PK parameter data will be listed, summarized and plotted.

There are no formal PK parameters for concentration data from Cycles 2 and 3 because these are single time points. However, metabolite to parent ratios will be explored.

Exploratory analyses of the relationship between plasma concentrations of parent drug and selected metabolites and/or PK parameters and AEs or PD biomarkers may be assessed by graphical methods and special summary tables. Exposure-response relationship may also be explored.

• Pharmacodynamic Biomarker Analysis:

Plasma levels of cytokines and chemokines will be evaluated as part of the PD biomarker analysis. Using the plasma samples, analysis will be performed for ctDNA and lipidomic profiling (capturing over 300 lipid species as determined by liquid chromatography-tandem mass spectrometry). Absolute and change from baseline results of biomarker analysis will be summarized descriptively and also presented on a plot.

[figure not shown]

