1.3.1 Electrocardiogram Schedule

Table 1-2	Electrocardiogram Schedule: Part 1 (All Patients) and Part 2 (Only
	for First 10 Patients in Each Tumor Type)

Sampling Time Point	Cycle 1 Day 1	Cycle 1 Day 2	Cycle 1 Day 6	Cycle 1 Day 14	Cycle 2 Day 1	Cycle 3 Day 1
Predose	\mathbf{X}^{\dagger}	Х	X^\dagger	X^\dagger	X^\dagger	\mathbf{X}^{\dagger}
1 hour (+ 15 minutes)	Х		Х	Х	Х	Х
2 hours (+ 15 minutes)	Х		Х	Х		
3 hours (+ 15 minutes)	Х		Х	Х		
4 hours (+ 15 minutes)	Х		Х	Х		
6 hours (+ 15 minutes)	Х		Х	Х		
8 hours (+ 15 minutes)	X ^a					
12 hours (+ 15 minutes)	X ^a					

† Within 30 minutes prior to dosing to allow for sitting blood pressure if needed.

^a Only for Part 1.

NOTE: For patients who will not undergo PK sampling in Part 2 of the study, a single ECG will be collected predose on Day 1 of each cycle up to Cycle 3.

After Cycle 3 Day 1, ECGs will be taken predose (within 30 minutes prior to dosing to allow for sitting blood pressure if needed) for all patients in both study parts, on Day 1 of every second cycle thereafter (i.e., Cycles 5, 7, 9, 11 etc.) and at the EOT/ED Visit.

1.3.2 Pharmacokinetic and Pharmacodynamic Sampling Schedule for Part 1 and Part 2

Table 1-3Pharmacokinetic Sampling Schedule Following Morning Dose –
Part 1 (All Patients) and Part 2 (Only for First 10 Patients in Each
Tumor Type)

Sampling Time Point	Blood Volume (mL)		Cycle 1 Day 2*	-	-	Cycle 1 Day 15**	•	Cycle 2 Day 8***	Cycl e 3 Day 1 ^b	Cycle 3 Day 8 ^{b,} ***
Predose (within 15 minutes prior to dosing)	1 × 4	х	х	Х	Х	Х	X	Xc	X	Xc
0.5 hour (± 5 minutes)	1×4	Х		Х	Х					
1 hour (± 5 minutes)	1×4	Х		Х	Х					
2 hours (± 5 minutes)	1×4	Х		Х	Х		Х		Х	
3 hours (± 5 minutes)	1×4	X		Х	Х					
4 hours (± 5 minutes)	1×4	Х		Х	Х					
6 hours (± 10 minutes)	1×4	Х		Х	Х					
8 hours (± 15 minutes) ^a	1 × 4	Х								
12 hours (\pm 30 minutes; Prior to evening dose) ^a	1×4	Х								

^{a.} Only for Part 1.

^{b.} Cycle 3 Days 1 and 8 samples only for patients in Part 2.

^{c.} Can be collected at home.

* Sample to be collected approximately 12 hours post Day 1 evening dose.

** Sample to be collected approximately 12 hours post Day 14 evening dose.

*** Sample to be collected approximately 12 hours post Day 7 evening dose.

Table 1-4	Pharmacodynamic Sampling Schedule – Part 1 and Part 2 (All
	Patients)

Assay	Blood Volume (mL)	Screening/Cycle 1 Day 1 Predose ^c			End of Treatment/Early Discontinuation
Chemokines, cytokines and lipids ^a	1 × 4	Х	Х	Х	Х

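### AUC(0-12), AUC(0-inf) and half-life are planned on Days 6 and 14, but sampling on those days stops at 6 h of a roughly 12 h dosing interval and no rule covers the gap

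*Combined protocol and SAP*

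**What the plan says.** Section 9.4.7.3 and the synopsis list Cmax, predose Cmin, Tmax, AUC(0-t), AUC(0-6), AUC(0-12), AUC(0-inf) and half-life, to be estimated "following the morning dose on Days 1, 6 and 14 of Cycle 1, as data permit". The next statement in Section 9.4.7.3 begins "Dose proportionality will be assessed using the power model for". It names Cmax, AUC(0-t), AUC(0-inf), AUC(0-6) and AUC(0-12), and ends "on Days 1, 6 and 14 of Cycle 1 for the parent compound". It does not repeat the condition about what the data permit. Accumulation ratios (Day 6/Day 1 and Day 14/Day 1) are planned for the same AUCs.

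In Table 1-3 the last post-dose row marked for Days 6 and 14 is "6 hours (± 10 minutes"). The 8 h row and the 12 h row (labelled "Prior to evening dose") are marked for Day 1 only, and a footnote limits them to Part 1. The Day 15 sample does not complete the Day 14 morning profile, because its footnote reads "Sample to be collected approximately 12 hours post Day 14 evening dose".

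The synopsis rationale and Section 2.1 state that "this suppository dosage form provides a slow and sustained release of idronoxil comparable to an intravenous infusion". No half-life or absorption rate is given. Section 9.4.7.3 leaves the details to the SAP, and no separate SAP text is in the document reviewed.

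**The concern.** AUC(0-12) on Days 6 and 14 needs concentrations out to 12 h, and half the interval is never sampled in any patient. Noncompartmental software will still return a number by fitting a terminal slope to the last few points and extending it. If the suppository is still releasing drug at 3 to 6 h, those points do not show the elimination phase, and the fitted half-life is too long.

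AUC(0-inf) has a second problem. After 10 earlier doses (Day 6) or 26 (Day 14), the area extrapolated to infinity includes what those doses left behind. It is neither the exposure from one dose nor comparable with Day 1.

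At stake are the secondary PK conclusions on dose proportionality and accumulation, and the PK data that the SSC may see (Section 7.1.2.1). Cohorts 2 to 4 may be enlarged to 8 patients specifically for PK estimation (Section 4.1.1).

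**Working it through.** **1. Does the schedule really stop at 6 h?** The marked cells of Table 1-3 are: Cycle 1 Day 1, 9; Day 2, 1; Day 6, 7; Day 14, 7; Day 15, 1; Cycle 2 Day 1, 2; Cycle 2 Day 8, 1; Cycle 3 Day 1, 2; Cycle 3 Day 8, 1. The sum is 31, which is the maximum stated in Section 8.5. With 8 h and 12 h samples on Days 6 and 14 it would be 31 + 4 = 35. The Day 6 and 14 profiles therefore have seven points: predose, 0.5, 1, 2, 3, 4 and 6 h.

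**2. Model.** The inputs from the protocol are twice-daily dosing (taken as 12 h; Table 6-1 requires at least 10 h) and the sampling times above. Two inputs are assumed because the protocol gives neither: half-life 1 to 12 h and absorption rate ka 0.5 to 2 per h. With k = ln 2/half-life, τ = 12 h and A a constant, the one-compartment steady-state profile is

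C(t) = A[e^(-kt)/(1 - e^(-kτ)) - e^(-ka·t)/(1 - e^(-ka·τ))].

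It follows that

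- AUC(0-τ) = A(1/k - 1/ka)
- AUC(0-inf) = A{1/[k(1 - e^(-kτ))] - 1/[ka(1 - e^(-ka·τ))]}, as if no evening dose followed
- the areas after 6 h come from the same integrals started at 6 h.

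Example with half-life 12 h, ka 0.5 and A = 1:

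- k = 0.0578, so AUC(0-τ) = 17.31 - 2.00 = 15.31.
- AUC(0-inf) = 34.62 - 2.00 = 32.62, and the ratio is 32.62/15.31 = 2.13.
- The area after 6 h is 0.7071 × 34.62 - 0.0498 × 2.00 = 24.38, so the share of AUC(0-inf) is 24.38/32.62 = 75%.
- The area from 6 to 12 h is 24.38 - 17.31 = 7.07, so the share of AUC(0-12) is 7.07/15.31 = 46%.

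Results over ka 0.5 to 2, the same on Days 6 and 14:

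| Half-life | AUC(0-12) after 6 h | AUC(0-inf) after 6 h | AUC(0-inf)/AUC(0-τ) |
|---|---|---|---|
| 1 h | 2%-13% | 2%-14% | 1.00-1.01 |
| 2 h | 13%-25% | 15%-29% | 1.02-1.05 |
| 4 h | 29%-37% | 38%-49% | 1.16-1.22 |
| 8 h | 39%-44% | 61%-66% | 1.57-1.66 |
| 12 h | 43%-46% | 72%-75% | 2.03-2.13 |

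**3. Terminal slope from 3, 4 and 6 h.** With slow absorption (ka 0.5), a log-linear fit gives a half-life of 8.0 h when the truth is 4 h, and 18.3 h when it is 8 h. The estimated AUC(0-inf)/AUC(0-τ) is then 1.70 and 2.97, against true values of 1.22 and 1.66. With ka 2 the fit is close to the truth (4.0 h and 8.1 h).

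**4. Effect on the power-model slope.** If half-life and absorption are the same at every dose, both distortions multiply every dose level by the same factor, and the slope is unchanged. Suppose instead that half-life doubles over the 3-fold range (800 to 2400 mg), with ka 1 and clearance held constant so that AUC(0-τ) stays proportional. Carry-over alone then adds to the AUC(0-inf) slope:

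- half-life 2 to 4 h: ln(1.173/1.024)/ln 3 = 0.136/1.099 = 0.12
- half-life 4 to 8 h: ln(1.599/1.173)/ln 3 = 0.310/1.099 = 0.28

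**5. Alternative for AUC(0-12).** Taking the same-day predose concentration as the 12 h value, with the linear-up/log-down rule, gives AUC(0-12) within about -4% to 0% of the truth over the whole assumed grid. No terminal slope is needed.

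**The case against.** The strongest reply has four parts.

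- **The plan is already conditional.** The parameter list applies only as far as the data allow, a power model can use only values that were estimated, and slope and extrapolation criteria are usual SAP content. This stands in part: such rules may yet be written. But the gap affects every patient by design, software will produce values unless told not to, and a SAP cannot supply samples that were never scheduled.
- **Most of the analysis is sound.** A reader might infer that dose proportionality on Days 6 and 14 as a whole rests on extrapolation. The documents do not support that. Three of the five measures (Cmax, AUC(0-6), AUC(0-t)) use observed samples only, and half-life is not a dose-proportionality measure.
- **The RP2D is untouched.** A reader might infer that the recommended dose is at risk. Table 3-1 sets it by DLT count and patient acceptability, Section 9.4.6.1 repeats the DLT basis, and Section 7.1.2.1 has the SSC look at PK only if available. PK is a secondary objective and all analyses are descriptive. This stands in full.
- **No bias in the slope is shown.** Under linear kinetics there is none, and with a half-life near 1 h the unsampled share is small. Both statements are right. But constant kinetics across doses is what a proportionality analysis is meant to examine, so it cannot be assumed in order to defend the measure.

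**Conclusion.** The point holds in a limited form. AUC(0-12), AUC(0-inf) and half-life on Days 6 and 14 are not supported by sampling that ends at 6 h, and the protocol states no rule for handling this.

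The size depends on a half-life that the protocol does not give. At the short end of the assumed range the problem is negligible; at the long end nearly half of AUC(0-12) and three quarters of AUC(0-inf) are unobserved. The unsampled share of AUC(0-12) stays below 50% throughout. That of AUC(0-inf) passes 50% only from a half-life somewhere between 4 and 6 h (52%-59% at 6 h). A release as slow as the rationale describes points away from the favourable end, but does not fix a value.

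Slope bias is conditional on dose-dependent kinetics. The consequence is confined to the secondary PK conclusions and the PK data shown to the SSC.

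**What to change.** Change Section 9.4.7.3 and the synopsis, and carry the rules into the SAP before database lock:

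- On Days 6 and 14, base dose proportionality and accumulation on Cmax and AUC(0-6). Predose concentration is no substitute in the accumulation ratio, since its Day 1 value is zero.
- Derive AUC(0-12) on Days 6 and 14 with the same-day predose concentration as the 12 h value, and state the steady-state assumption. The scheduled samples taken before the morning dose on Days 6 and 14 and on Day 15 allow a descriptive check. The substitution is not available for Part 2 Day 1, where no earlier dose exists.
- Drop AUC(0-inf) and half-life on Days 6 and 14. Report them only for Day 1 of Part 1, where sampling reaches 12 h, with a prespecified limit on the extrapolated share. A limit of 20% would serve; it is the analyst's choice and has no source in the protocol.

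The cost is a wording change in the protocol and SAP, fewer PK parameters on two days, and reliance on steady state and on intervals near 12 h. With a minimum gap of 10 h, the overnight interval could reach 24 - 10 = 14 h, so the actual time since the previous evening dose should be checked against the dosing diary. No extra samples are needed.

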Pharmacokinetic Measurem	ent												
Blood sample for PK ^z	Х		Х	Х		Х							
Pharmacodynamic Biomark	ker As	sessment							-				
Blood sample for biomarkers ^{aa}			Х								Х		
Archived tissue collection if available (Optional) ^{bb}													
Fresh tissue biopsy after Cycle 3 treatment (Optional) ^{bb}						х							
Treatment Administration													
NOX66 ^{cc}	Х	Х		Х	Х		Х	Х		Х			
EBRT (1-10 days) dd													

AE = adverse event; BPI-SF = Brief Pain Inventory – Short Form; C1D1 = Cycle 1, Day 1; COVID-19 – coronavirus disease 2019; CT = computerized tomography; d = day(s); EBRT = external beam radiotherapy; ECG = electrocardiogram; ECOG = Eastern Cooperative Oncology Group; ED = Early Discontinuation; EORTC-QLQ-C30 = Quality of life Questionnaire for Cancer Patients; EOT = End of Treatment; FACT-P: Functional Assessment of Cancer Therapy – Prostate; FSH = follicle-stimulating hormone; Gy = Gray; mCRPC = metastatic castration-resistant prostate cancer; MRI = magnetic resonance imaging; PCWG-3 = Prostate Cancer Working Group 3; PEQ = Patient Experience Questionnaire; PK = pharmacokinetics; PRO = Patient Reported Outcome; PSA = prostate-specific antigen; RECIST = Response Evaluation Criteria in Solid Tumors; SAE = serious adverse event; SARS-CoV-2 = severe acute respiratory syndrome coronavirus 2; SRE = skeletal-related events; SSE = symptomatic skeletal events; WBC = white blood cell; WOCBP = women of childbearing potential

- † Patients will receive the study drug from Cycle 1 Day 1 and may continue to receive the study drug until disease progression, unacceptable toxicity, withdrawal of consent, start of new anticancer therapy, withdrawal of the patient by the Investigator or termination of the study by the Sponsor.
- ‡ From Cycle 3 onwards, study drug for 2 cycles will be dispensed every second cycle (i.e., Cycles 5, 7, 9, 11 etc.). From Cycle 5 onwards, on-site visits will occur on a 28-day (4 weekly) basis, i.e., patients will visit the clinical unit every second cycle. After Cycle 5, the next on-site visit will therefore be Cycle 7, followed by Cycle 9, etc. until the patient completes the study treatment period or discontinues from the study, whichever comes first.
- § The procedures listed and schedule followed for Cycle 4 will be assessed at all cycles without an on-site visit (unless otherwise specified).

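### The Cmin accumulation ratios divide by a sample drawn before the first NOX66 dose, and the Cmax and AUC ratios for Day 8 of Cycles 2 and 3 would rest on a single sample

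*Combined protocol and SAP*

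**What the plan says.** The synopsis lists the parameters to be estimated "following the morning dose on Days 1, 6 and 14 of Cycle 1, as data permit: C_{max}, C_{min} (predose), T_{max" and so on, which makes Cmin the predose value on each of those days. Section 9.4.7.3 gives the same list and the same days ("following the morning dose on Days 1, 6 and 14 of Cycle 1, as data permit").

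Section 9.4.7.3 then continues: "If data permits, accumulation ratios will be calculated for parent compound and selected metabolites", for Cmax, Cmin, AUC(0-t), AUC(0-inf), AUC(0-6) and AUC(0-12). The days are given as "e.g., Day 14/Day 1 and Day 6/Day 1) and Day 8 of Cycles 2 and 3". Day 1 is the only reference day named, and no reference is given for Day 8.

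Three other statements bear on this:

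- Table 1-3 times the first sample of each profile as "Predose (within 15 minutes prior to dosing", and the footnotes to the Schedule of Activities say: "Patients will receive the study drug from Cycle 1 Day 1".
- Table 1-3 has one sample on Day 8 of Cycle 2 and one on Day 8 of Cycle 3, each about 12 hours after the Day 7 evening dose. Cycle 3 is sampled in Part 2 only.
- Later in section 9.4.7.3: "There are no formal PK parameters for concentration data from Cycles 2 and 3 because these are single time points".

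**The concern.** An accumulation ratio compares exposure after repeated dosing with exposure after the first dose. For Cmax and AUC on Day 1, the samples after the first dose supply that reference. For a Cmin defined as predose they do not, because the Day 1 predose sample describes a patient who has not yet had the drug. The abbreviations list defines Cmin instead as the minimum observed concentration, but with the predose sample included the Day 1 minimum is that same sample.

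The Day 8 part of the sentence fails for a different reason. It carries the full list of six parameters into a day with one sample.

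At stake is the trough ratio. It is the one derived accumulation measure that could be followed from the 14 days of twice-daily dosing in Cycle 1 into the 7-days-on, 7-days-off cycles. As written, the plan leaves it without a valid denominator, and a programmer would have to choose one.

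**Working it through.** **Check of the reading of Table 1-3.** Marks per column are: Cycle 1 Day 1, 9; Day 2, 1; Day 6, 7; Day 14, 7; Day 15, 1; Cycle 2 Day 1, 2; Cycle 2 Day 8, 1; Cycle 3 Day 1, 2; Cycle 3 Day 8, 1. The sum is 9 + 1 + 7 + 7 + 1 + 2 + 1 + 2 + 1 = 31, which reproduces the maximum of 31 samples in section 8.5. The single Day 8 sample is therefore not an artefact of the broken table.

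**Doses taken before each predose sample.** With twice-daily dosing from Day 1, the number is 2 × (day − 1): Day 1, 0; Day 2, 2; Day 6, 10; Day 14, 26.

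**Cmin ratio as planned.** The ratio is the Day 6 or Day 14 predose concentration divided by the Day 1 predose concentration. After 0 doses the expected denominator is 0 or below the lower limit of quantification (LLOQ). With 0 the ratio is undefined. Section 9.4.7.3 gives no rule for values below quantification, so suppose that LLOQ/2 or LLOQ were substituted:

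| Later trough (assumed) | Ratio with LLOQ/2 | Ratio with LLOQ |
|---|---|---|
| 2 × LLOQ | 4 | 2 |
| 10 × LLOQ | 20 | 10 |
| 50 × LLOQ | 100 | 50 |

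These values are set by the assay limit and the substitution rule. They do not measure accumulation.

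**Day 8 of Cycles 2 and 3.** A trapezoidal AUC needs at least two points, and one sample about 12 hours after a dose cannot identify a peak. So Cmax, AUC(0-t), AUC(0-inf), AUC(0-6) and AUC(0-12), 5 of the 6 listed parameters, cannot be derived. Only a trough-type ratio can be formed, and only once a post-dose denominator is named.

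**Post-dose denominators already sampled.** There are two:

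- The Day 1 12-hour sample, drawn before the evening dose, follows 1 dose and is taken in Part 1 only.
- The Day 2 predose sample follows 2 doses and is taken in both parts ("Sample to be collected approximately 12 hours post Day 1 evening dose").

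**How much the choice matters.** The documents give no half-life, so this is an illustration. Assume one compartment, a 12-hour interval and steady state, and let e = 2^(−12/t½). Relative to the first-dose trough, the steady-state trough is 1/(1 − e) and the Day 2 trough is 1 + e. The steady-state trough relative to Day 2 is the first divided by the second.

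| Assumed t½ | e | Relative to first-dose trough | Day 2 trough relative to first dose | Relative to Day 2 trough |
|---|---|---|---|---|
| 6 h | 0.25 | 1.33 | 1.25 | 1.07 |
| 12 h | 0.50 | 2.0 | 1.50 | 1.33 |
| 24 h | 0.707 | 3.4 | 1.707 | 2.0 |

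The Day 2-based ratio is always the smaller, so a single unlabelled ratio could mean either quantity.

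**The case against.** The best defence is that the section limits itself. The ratios are conditional on the data, the Day 1 denominators follow an e.g., details are referred to the SAP, and the statement about Cycles 2 and 3 would stop a programmer from attempting Cmax or AUC on Day 8. Part of this stands: the Day 8 wording is more likely to cause confusion than a wrong number. The rest does not cure the fault. A data condition covers missing or unquantifiable samples, whereas here the schedule never supplies the data even if collection is complete. No other denominator is named, and the text available for review holds no further PK rule.

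A second argument is about importance. All analyses are descriptive. MTD and RP2D rest on DLT counts, no accumulation threshold enters the dose decisions, and the ratio is not named among the exposure endpoints. That is correct, and it limits the point to a repair of the analysis text.

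Two stronger readings are tempting, and the documents do not support either:

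- A reader might infer that drug accumulation cannot be assessed at all. Table 1-3 samples from predose to 6 hours on Days 1, 6 and 14 in both parts, so the Day 6 and Day 14 ratios for Cmax and AUC(0-6) can be computed. Section 9.4.7.3 also summarises, lists and plots concentrations by day and time, so the troughs will be visible side by side.
- A reader might infer that the Cmin ratio is undefined in every patient for all eight analytes. That assumes every Day 1 predose value is zero or below quantification. Section 8.2.2.4.2 warns that soya isoflavones may interfere with the assay and permits trace amounts, so an occasional non-zero value is possible; it would give a ratio, but not one that measures accumulation. The plan also speaks of up to seven metabolites, so the number of analytes is not fixed.

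**Conclusion.** The rule is wrong as written. The Cmin accumulation ratios for Day 6 and Day 14 are undefined or uninformative because their only named denominator precedes treatment. For Day 8 of Cycles 2 and 3, five of the six listed parameters cannot be derived, and listing them contradicts the section's own statement about those cycles. The loss is confined to the trough accumulation ratio.

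The first conclusion rests on the predose definition, the timing in Table 1-3 and the expectation of no quantifiable drug before the first dose. The second rests on the sample count, which reproduces the protocol's total of 31. The fold figures rest on assumed half-lives and a model without absorption. The protocol describes slow release, and doses may be only about 10 hours apart, so the figures show why the denominator must be named and do not predict idronoxil or metabolite accumulation.

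**What to change.** Amend section 9.4.7.3 and the synopsis together, and carry the rule into the SAP before database lock:

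1. **Part 1.** Define the Cmin accumulation ratio with the Day 1 12-hour concentration, before the evening dose, as denominator. The numerators are the Cycle 1 Day 6, Day 14 and Day 15 troughs and the Cycle 2 Day 8 trough.
2. **Part 2.** There is no Day 1 12-hour sample here, and this is the only part with Cycle 3 samples. Use the Day 2 predose concentration as denominator for the Cycle 1 troughs and for the Day 8 troughs of Cycles 2 and 3. Label the result as the ratio to the Day 2 trough.
3. **Comparison of parts.** Report the Day 2-based ratio in Part 1 as well. Do not pool it with the first-dose ratio.
4. **Day 8.** Delete Cmax and all AUCs from the ratios for Cycles 2 and 3, keep the trough ratio only, and reconcile this with the statement that those cycles give no formal parameters.

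The cost is wording and a changed programming rule; no new samples are needed. The drawback is that the Day 2-based ratio understates accumulation relative to the first dose, and that no Cycle 3 trough can have a first-dose reference.
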